Protocol

1. Title:

Investigating the Influence of Catheter Advancement Techniques on Needle Tip Movement During Intravenous Insertion

2. Investigators

PI: [name]

Co-PI: [name]

Co-Investigators:

[name]

3. Background and Significance:

Previous studies have explored various aspects of intravenous (IV) insertion techniques, focusing on factors such as needle size, angle of insertion, and patient comfort. However, there is limited research on the influence of different catheter advancement techniques on needle tip movement in the process of advancing the catheter off the needle. The proposed study aims to fill this gap by investigating whether needle tip movement during catheter advancement is affected by whether the individual performing the insertion pushes the catheter off the needle themselves (either one handed or two handed) or if the catheter is advanced off the needle by another person.

4. Specific Aims:

Aim 1: To assess the impact of three different catheter advancement techniques on needle tip movement during intravenous insertion.

Hypothesis 1: The needle tip will exhibit less movement during catheter advancement when performed by another individual compared to advancement by the inserter.

5. Research Plan:

Study Design: This study will employ a within-subject, crossover design where each participant serves as their own control. Each participant will do intravenous catheter insertions using an instrumented IV catheter and peripheral vascular access simulator using three different catheter advancement techniques: self-advancement (one-handed), self-advancement (two-handed), and catheter advancement by another individual. The order of techniques will be randomized.

Setting: The study will take place in the simulation laboratory or a clinician break area in the hospital.

Study Subjects: Participants will include adult volunteers who in the course of their work or training place peripheral IV catheters. The sample size will be determined based on power analysis to detect significant differences in needle tip movement.

Main Outcome Measures: The main outcome measure will be needle tip movement during catheter advancement, measured to within 0.2mm accuracy using a UF built IV simulator equipped with tracking technology.

Analyses: Statistical analyses, such as paired t-tests or non-parametric equivalents, will be conducted to compare needle tip movement between different catheter advancement techniques. Additionally, potential confounding variables, such as participant demographics or experience level, will be accounted for in the analyses.

PARTICIPANT SELECTION CRITERIA:

We propose including 50 subjects, 18 years of age and older. Potential subjects will be approached via email listservs to inquire about potential interest in participating in the study. If they express interest, their information will be passed along to members of the study team. Consent will be obtained from the subject after the study has been explained and all questions have been answered. 50 subjects are anticipated to be enrolled.

Inclusion criteria shall be as follows:

- 1) 18 years of age or older
- 2) Willing to consent to the study
- 3) has some experience placing IV catheters

Exclusion criteria shall be as follows:

- 1) Subject refuses to consent
- 2) Younger than 18 years of age
- 3) **No experience inserting IV catheters**

After consent, the following information will be gathered from the participant:

- Demographic information (age, sex)
- Educational Status
- IV catheter experience placement

The targeted study population will include adult volunteers 18 years or older who in the course of their work or training place peripheral IV catheters. The setting in which the research will take place is the Harrell Medical Education Building (HMEB) Simulation Laboratory or in a clinical break area.

UF/Shands students and staff are included within the targeted study population as they are primarily involved in the procedure- intravenous catheter insertion- under examination. Pregnant women will be considered for this project as part of the general population and not as a targeted study population. Safeguards to minimize any coercion or undue influence include potential subjects being informed of the study via an email listserv and having them voluntarily approaching the research team indicating interest in inclusion in the research. Safeguards against coercion of students include: Investigator is not their instructor or advisor, the research is not part of a course curriculum, and there is no course credit for research participation.

Potential subjects will be approached via email listserv advertising to inquire about potential interest in participating in the study. If they express interest, their information will be passed along to members of the study team.

Protected health information will not be accessed for this project. Measures taken to protect the confidentiality of subjects include: Computer-based files will only be made available to personnel involved in the study through the use of access privileges, passwords, and encryption; Whenever feasible, identifiers will be removed from study-related information.

Consent will be obtained by the research team including, [name] (PI), [name] (Co-PI Investigator), [name] (Co-Investigator), and [name] (Co-Investigator). Subjects will be asked to consent following recruitment and prior to commencing the study and collecting data. The Informed Consent form will be used as the summary of consent discussion. Subjects will be given the opportunity to take the consent home to discuss with family members, friends, and/or someone knowledgeable about the protocol. Coercion or unduly influencing subjects during the consent process will be minimized by emphasizing the voluntary nature of this study with additional reassurance that participants can withdraw from the study at any time without penalty. Additionally, there will be an ample opportunity for questions and no incentives will be provided through the entirety of the study.

DESIGN

STUDY PROCEDURES:

After a particular individual is identified, the research team will directly contact the subject to explain the nature of the research and the reason for contacting.

Then, an informed consent form will be provided to include details of the investigation and intended procedures. After clarifying potential questions, the treating team will be notified about the inclusion. Those that consent to participate will undergo the following procedures:

Study course:

1. Participant Recruitment and Consent:
 - i. Identify potential adult volunteers aged 18 or older involved in peripheral IV catheter insertion.
 - ii. Approach potential subjects via email listservs, inviting them to participate.
 - iii. Explain the study details and obtain informed consent from interested participants.
 - iv. Emphasize voluntary participation, the ability to withdraw without penalty, and address any questions or concerns.
2. Study Setup and Preparation:
 - i. Set up the study simulator equipment in the Harrell Medical Education Building Simulation Laboratory or in a clinical break area.
 - ii. Ensure all necessary equipment, including the instrumented IV catheter and peripheral vascular access simulator, are prepared and functional.
3. Participant Orientation:
 - i. Orient participants to the study procedures, including the use of the IV simulator and catheter advancement techniques.
 - ii. Provide instructions on the three different catheter advancement techniques: self-advancement (one-handed), self-advancement (two-handed), and catheter advancement by another individual.
4. Data Collection:
 - i. Each participant will perform up to 3 IV catheter insertions using each of the specified techniques.
 - ii. Participants will use the instrumented IV catheter to insert into the peripheral vascular access simulator.
 - iii. Needle tip movement from intent of catheter advancement to 5mm of advancement off the needle will be measured with 0.2mm accuracy using the electromagnetic tracking technology of the simulator.

- iv. Data collected will include needle movement after simulated vein puncture and during catheter advancement off the needle (in mm) which will be recorded within the simulation program and output as a de-identified Excel file.
 - v. The order of catheter advancement techniques will be randomized to minimize bias.
5. Interim Analysis/Results and Conclusion (if applicable):
- i. Evaluate the study progress and any emerging trends or patterns in the data.
 - ii. Consider any necessary adjustments to study procedures or sample size based on interim findings.
 - iii. Draw conclusions based on the statistical analysis and address the study hypothesis. Discuss implications for clinical practice and potential areas for further research.

Study Visit Schedule (total time 15 minutes):

Participant arrives at the simulation setting.

Participant undergoes orientation and consent. This includes orientation to study procedure and equipment, explanation of catheter advancement techniques, and informed consent process.

Following consent, patient demographic information and educational status will be obtained. Total time required: Approximately 10 minutes.

Participant performs IV catheter insertion using 3 techniques: 1 (Self-advancement single hand), technique 2 (Self-advancement both hands), and technique 3 (second person assisted) in randomized order. Total time required: Approximately 5 minutes. Participant's participation is concluded.

In this study, the observation to be carried out is the total distance of needle tip movement while performing intravenous catheter insertions using three different catheter advancement techniques including: Self-advancement with one hand; Self-advancement with two hands; Catheter advancement by another individual.

There is no placebo or other treatment involved in this study. The experimental control is the comparison between the three different catheter advancement techniques. Each participant serves as their own control in a within-subject, crossover design. The order in which participants perform IV catheter insertions using the different techniques is randomized, minimizing potential biases. This randomization helps ensure that the results are not influenced by the order in which the techniques are tested.

Following the consent process, the information about subjects that will be obtained from subjects is demographic data limited to age and sex as well as education status and clinical experience as well as their preferred catheter advancement technique for routine catheter placement. In addition, participants will be asked if they are familiar with the three different techniques, and what their preferred method is for difficult catheter placement. This information will be obtained by the research team prior to the start of the study at the HMEB Simulation Laboratory.

ADMINISTRATIVE RESPONSIBILITIES:

There is no Data Safety Monitoring Board (DSMB) or an oversight committee for this research project. Given the very low risk to the participants, no formal plan to monitor subject safety will be employed.

STATISTICAL METHODS, DATA ANALYSIS, AND INTERPRETATION:

In our theoretical pilot study, the mean of the needle tip movement for each group was made 3, 2, and 1 mm, respectively. We calculated the sample size to detect a mean paired difference of 0.3 (10% of group 1) with an estimated standard deviation of differences of 0.5 between the group 1 and group 3. Given a significance level of 0.05 with a power of 90%, and dropout of 10%, we finally targeted the enrollment of 30 participants.

The Kolmogorov-Smirnov test will be performed for the normality test. For continuous variables, we will use RMANOVA if they follow a normal distribution, otherwise we will compare means with the Friedman test. Categorical data will be compared with Chi-square test. For the primary outcome, the mean lengths of the needle tip movement will be compared using the repeated-measures ANOVA or non-parametric equivalent. And then we will perform the Bonferroni correction for post hoc test. A p-value less than 0.05 was considered significant. Statistical analyses were conducted using SPSS.

The analyses will involve comparing needle tip movement measurements obtained from each participant across the three different catheter advancement techniques. Statistical software such as SPSS will be used to perform the analyses and generate descriptive statistics and inferential results. Data analyses will be conducted primarily by the research team, including [name], [name], and [name].

Interim analyses may be conducted to assess the progress of the study and evaluate any emerging trends or safety concerns. However, given the nature of the study and the minimal to no risk involved, formal stopping rules are not anticipated.

DATA STORAGE AND DE-IDENTIFICATION PLANS:

All data will be stored on departmental password protected encrypted share drives or in UF approved cloud environments (i.e. LabArchives) that only the study staff will have access to. At the conclusion of the data collection and analysis, all data will be permanently de-identified.

6. Possible Discomforts and Risks:

There are minimal (clean needle stick) risks to the participants as a result of the study. No identifiable information is being collected ameliorating any additional risk due to disclosure of identifiable information.

7. Potential Benefits:

There is no potential for direct benefits to participants beyond potentially objectively identifying a best technique for them.

The research study will benefit future populations by informing them of a technique which may indirectly improve quality of patient care and reduce IV catheter insertion failure.

8. Conflict of Interest:

No investigators have a conflict of interest beyond authorship in any resulting publication(s).

9. References:

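### No rule ties the primary analysis to Hypothesis 1: a non-directional three-way test with unnamed post hoc pairs leaves a split result undecided and spends power on one- versus two-handed advancement

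*Combined protocol and SAP*

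**What the plan says.** Section 4 (Specific Aims) has one aim and one hypothesis. Aim 1 is three-way and has no direction: "To assess the impact of three different catheter advancement techniques on needle tip movement during intravenous insertion". Hypothesis 1 is directional: "The needle tip will exhibit less movement during catheter advancement when performed by another individual compared to advancement by the inserter". Section 3 (Background and Significance) makes clear that the inserter may advance the catheter with one hand or with two. The hypothesis therefore sets one technique against two.

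The section on statistical methods states, for the primary outcome, that "the mean lengths of the needle tip movement will be compared using the repeated-measures ANOVA or non-parametric equivalent". It continues: "And then we will perform the Bonferroni correction for post hoc test". It names neither the pairs nor the divisor. The threshold is given as "A p-value less than 0.05 was considered significant", without saying whether tests are one- or two-sided. The analyses paragraph of section 5 is looser: "Statistical analyses, such as paired t-tests or non-parametric equivalents, will be conducted to compare needle tip movement between different catheter advancement techniques". It names no pair either.

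The sample-size sentence is built on one pair, "with an estimated standard deviation of differences of 0.5 between the group 1 and group 3". In the technique order of the visit schedule, that is one-handed versus assisted. The last item of the study course says that conclusions will address the hypothesis, but no section says which result would support it.

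**The concern.** The primary test and the only hypothesis ask different questions. The omnibus test asks whether any of the three means differ. It responds equally to assistance being better, to assistance being worse, and to a difference between the two self techniques alone. The hypothesis asks whether assistance is better than advancement by the inserter.

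The post hoc step can supply the missing direction, but the plan does not say which pairs bear on the hypothesis or how to combine them. If assistance beats one-handed but not two-handed advancement, the authors would have to decide after seeing the data whether the hypothesis was supported. If Bonferroni is applied to all three pairs, which is its usual meaning here, part of the error allowance goes to one- versus two-handed, a comparison the hypothesis does not mention.

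**Working it through.** **Inputs.** From the section on statistical methods: paired difference 0.3 mm, SD of differences 0.5 mm (given for group 1 versus group 3 only), alpha 0.05, power 90%, dropout 10%, target 30, planning means 3, 2 and 1 mm. The participant selection section gives 50 participants. Completers are 30 × 0.9 = 27, or 50 × 0.9 = 45.

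**Assumptions.** SD 0.5 mm for every pair, normal data, and post hoc tests on all three pairs, two-sided at 0.05/3.

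**1. The plan's own figure.** n = ((z for alpha + z for power) × SD / difference)².
- Two-sided z: ((1.960 + 1.282) × 0.5 / 0.3)² = 5.403² = 29.2, so 30 before dropout and 30/0.9 = 33.3, so 34, after.
- Two-sided t: 32, or 36 after dropout.
- One-sided t: 26, or 29 after dropout.

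The target of 30 is thus reached approximately by a one-sided t-test with dropout, or by a two-sided z calculation without it. Either way it is a calculation for one pair, not for a three-level test or two contrasts.

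**2. What the omnibus test responds to.** Its noncentrality is n × Σ(mean − grand mean)² / error variance, where the error variance is 0.5²/2 = 0.125. Means are in the order one-handed, two-handed, assisted.
- Assistance 0.3 mm worse than both (2.0, 2.0, 2.3): squared deviations 0.01 + 0.01 + 0.04 = 0.06, so 27 × 0.06 / 0.125 = 12.96.
- Assistance 0.3 mm better than both (2.3, 2.3, 2.0): again 0.06, so again 12.96.

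The test cannot tell these two cases apart.

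**3. The full sequence, simulated.** 20,000 trials per row, 27 completers. The last three columns give the share of trials in which assisted is significantly lower at 0.05/3; the last also requires a significant omnibus test.

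| Means (one-handed, two-handed, assisted) | Omnibus p<0.05 | Below one-handed | Below two-handed | Below both |
|---|---|---|---|---|
| 2.0, 2.0, 2.3 | 89% | 0% | 0% | 0% |
| 2.3, 2.0, 2.3 | 89% | 0.8% | 0% | 0% |
| 2.0, 2.3, 2.3 | 89% | 0% | 1.0% | 0% |
| 2.3, 2.0, 2.15 | 78% | 18% | 0% | 0% |
| 2.3, 2.0, 2.0 | 89% | 71% | 0.9% | 0.9% |
| 2.3, 2.3, 2.0 | 89% | 71% | 72% | 57% |
| 2.0, 2.0, 2.0 | 5% | 0.8% | 0.9% | 0.1% |
| 3, 2, 1 | 100% | 100% | 100% | 100% |

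In the first three rows assistance is better than neither technique. The omnibus test is significant in 89% of trials, but a pair favouring assistance appears in about 1% or less. In row four the 18% is a true difference of 0.15 mm. Row five is the split case: the 71% is a correct detection against one-handed, and the plan does not say what it means for the hypothesis.

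**4. Power when the hypothesis is true for both (row six).** Chance of showing both contrasts:

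| Completers | Omnibus, then Bonferroni over three pairs | Holm over two contrasts |
|---|---|---|
| 27 | 57% | 75% |
| 45 | 88% | 95% |

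Repeated runs at 27 completers vary by about one point (56 to 57%, and 74 to 75%). The gain is 75 − 57 = 18 points at 27 completers and 95 − 88 = 7 points at 45.

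**5. The two readings of the inserter are not interchangeable.** A single contrast of assisted against the average of the self techniques has about 93% power at 27 completers when both differ by 0.3 mm. With means 3, 2 and 2 mm that contrast is significant in about 100% of trials, although assistance is then no better than two-handed advancement.

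**The case against.** The strongest defence is that the plan does not stop at the omnibus test. A three-level ANOVA followed by Bonferroni is conventional and valid, it fits Aim 1, and the post hoc tests carry a sign. The study procedures also describe the comparison among all three techniques as the experimental control, so one- versus two-handed is within the stated scope. This stands.

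A reader might infer from the 89% that the trial would usually report support for a false hypothesis. The documents do not bear that out. No section treats a significant omnibus result as support for Hypothesis 1, and the planned pairs, if all three are run, remove nearly all of that risk. Nor should a reader take it as stated that all three pairs will be tested, since the text names none. It would also be wrong to say that the study considers only one-handed versus assisted; that restriction belongs to the sample-size sentence.

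Three further points stand in part. The power loss comes largely from the Bonferroni divisor, and it is much smaller if 50 participants are enrolled. Under the planning means of 3, 2 and 1 mm both approaches succeed in about 100% of trials; but the plan calls that pilot theoretical and sizes the study for 0.3 mm. Lastly, the documents do not settle whether the inserter means each self technique or their average, so a reviewer cannot choose for the investigators. None of this supplies the missing rule for a split result.

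**Conclusion.** The point holds as a gap between hypothesis and analysis, not as a high false-positive rate. The omnibus test alone cannot show Hypothesis 1, the post hoc pairs that could are unnamed, and no rule covers a split result. With true effects of 0.3 mm against both self techniques, the cost is about 18 percentage points in the chance of showing both contrasts at 27 completers, and about 7 at 45. These figures rest on an SD of differences of 0.5 mm for every pair, which the plan gives for one pair only, on normal data, and on Bonferroni over all three pairs. The missing rule for a split result depends on none of these assumptions. The change is inexpensive and worth making before the data are analysed.

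**What to change.** In the section on statistical methods:

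- Make two planned within-participant contrasts primary, assisted versus one-handed and assisted versus two-handed, tested two-sided with Holm at 0.05.
- State that a claim about the inserter in general needs both contrasts to be significant in favour of assistance. If only one is, the conclusion names that comparison alone.
- If the investigators mean the average of the two self techniques, say so and pre-specify that single contrast instead.
- Keep the omnibus test and one- versus two-handed as secondary analyses, so that Aim 1 is still covered.
- Align the paired-test wording in section 5 with this.

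The cost is wording only, with no new data or participants. One- versus two-handed loses primary status, and a win over one self technique no longer supports the whole hypothesis. When assistance truly beats only one technique, Holm tests the other at up to 0.05 two-sided, so a false finding in favour of assistance can reach 0.05/2 = 2.5%, compared with about 0.9% under the three-pair correction. That is still within the overall 0.05.

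### Does the wording of the outcome as a total distance make it grow with time and with the number of insertions, and so bias the comparison of techniques?

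*Combined protocol and SAP*

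**What the plan says.** The outcome is described in several places, in different words.

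- Research Plan, Main Outcome Measures: "The main outcome measure will be needle tip movement during catheter advancement".
- Study course, Data Collection, item iii, sets the window: "Needle tip movement from intent of catheter advancement to 5mm of advancement off the needle will be measured with 0.2mm accuracy". It applies to every technique.
- Data Collection, item iv, lists the recorded data more loosely, as movement after the simulated vein puncture and during advancement, in mm.
- Data Collection, item i: "Each participant will perform up to 3 IV catheter insertions using each of the specified techniques".
- Text after the Study Visit Schedule: "the observation to be carried out is the total distance of needle tip movement while performing intravenous catheter insertions".
- Statistical Methods: "For the primary outcome, the mean lengths of the needle tip movement will be compared using the repeated-measures ANOVA or non-parametric equivalent".

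For planning, "the mean of the needle tip movement for each group was made 3, 2, and 1 mm, respectively". The target is a mean paired difference of 0.3 mm with a standard deviation of differences of 0.5 mm. No section says whether movement means path length or displacement, how repeat insertions become one value per technique, or that window duration is recorded.

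**The concern.** A path length summed over tracked positions has two awkward properties. It picks up position error at every sample, so it lengthens with time even when the tip is still. If it is also summed over insertions, it rises with their number. The window ends at 5 mm of catheter travel and not at a fixed time, and the insertion count has a ceiling but no fixed value. If one technique takes longer, or has more insertions counted, the repeated-measures ANOVA would attribute the excess to technique. Randomising the order cannot remove this, because the time a technique takes belongs to the technique. The direction is not known in advance, so the artefact could mimic or hide the advantage that Hypothesis 1 expects for the second person. The stated accuracy of 0.2 mm is also two thirds of the target (0.2/0.3 = 0.67).

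**Working it through.** **The plan's own figures.** Ten per cent of the group 1 mean is 0.1 × 3 = 0.3 mm, as stated. The two-sided paired formula gives n = ((1.960 + 1.282) × 0.5/0.3)² = 29.2, so 30 before dropout. Whether the stated 30 already includes the 10% dropout is a separate matter and does not bear on this point.

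**Number of insertions.** Inputs: planning means of 1, 2 and 3 mm, taken as per-insertion values, and the 0.3 mm target.

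- If insertions are summed, one extra adds 1, 2 or 3 mm, which is 1/0.3 = 3.3, 2/0.3 = 6.7 or 3/0.3 = 10 times the target.
- A net share of 0.3/1 = 30%, 0.3/2 = 15% or 0.3/3 = 10% of participants one insertion short under one technique would then shift the mean by 0.3 mm.
- If the value analysed is the mean per insertion, an unequal count changes its precision but not its expected size, and the shift from counting is 0.

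The first two lines need both summing and counts that differ by technique. The plan states neither, and the cap of 3 is the same for all techniques.

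**Duration, real movement.** If path length accrues at a constant rate, a window 30%, 15% or 10% longer adds 0.3 mm at means of 1, 2 or 3 mm. A 0.3 mm shift would be significant with probability 0.89 at n = 30 (two-sided 0.05, SD 0.5). But tip travel that really occurs because a technique takes longer is part of that technique's effect, not bias.

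**Duration, tracker noise.** The documents give no sampling rate, no sample-to-sample error and no step time, so all three are assumed. With independent Gaussian error of SD s per axis, a still tip gains an expected 4s/√π per sample. A lag-one correlation of 0.9 multiplies this by √0.1.

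| s (mm), as share of 0.2 mm | Gain per sample (mm), independent | Extra samples to reach 0.3 mm, independent | Same, correlation 0.9 |
|---|---|---|---|
| 0.01 (5%) | 0.0226 | 13.3 | 42.0 |
| 0.02 (10%) | 0.0451 | 6.6 | 21.0 |
| 0.05 (25%) | 0.1128 | 2.7 | 8.4 |
| 0.10 (50%) | 0.2257 | 1.3 | 4.2 |

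In simulation (4000 runs per case, smooth one-way movement of 1 to 3 mm), lengthening the window from 50 to 100 samples raises path length by 0.60 to 11.2 mm with independent error and by 0.11 to 3.5 mm with correlated error. The range is about 100-fold (11.2/0.11), and its low end is under 0.3 mm. The high end fits poorly with the planning values: over 50 samples (49 steps) a still tip would already show 49 × 0.1128 = 5.5 mm or 49 × 0.2257 = 11.1 mm, against planned means of 1 to 3 mm. The 0.2 mm is an accuracy, not a jitter figure, and a constant offset cancels in any measure of movement.

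**Would maximum displacement cure it?** In the same one-way model it rises by at most 0.04 mm when the window doubles. That model lets no real movement occur in the extra time. If the tip instead wanders as a three-dimensional random walk, scaled to a mean maximum displacement of 1, 2 or 3 mm at 50 samples, doubling the window adds about 0.4, 0.9 or 1.3 mm. Each exceeds 0.3 mm. The advantage therefore depends on the motion model, which the documents do not supply.

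**The case for a change.** The best case for a change is this. The only words that hint at how movement becomes a number do suggest a length. Accumulated tracker error, unlike real tip travel, is no part of any technique's effect, and averaging over insertions does not remove it. The visit schedule allots about 5 minutes to the insertions. Nine of them would leave 300/9 ≈ 33 seconds each, so fewer than three per technique is plausible. The plan also allows a look at emerging trends and adjustment of procedures, so an undefined metric could be settled after data are seen. If the simulator's file holds only a summary in mm, displacement could not be recovered later. A few sentences would close all of this.

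What stands is that the metric and the way insertions are combined are not written down, and that noise would inflate a path length to some degree. What does not stand is the step to a bias in this trial. Total distance appears once, in a general description, and can equally mean the overall distance from start to end. The analysis section speaks of means. Nothing predicts that counts will differ by technique. The size of any noise effect comes from assumed inputs and not from the documents. Replacing path length with maximum displacement would also discard back-and-forth motion inside the vein, which the investigators may well want to capture.

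**Conclusion.** The concern does not call for a change. The text shows missing operational detail, not a rule that biases the comparison. The window is settled by Data Collection item iii, with a common start event and a common 5 mm endpoint, and the looser phrases elsewhere are to be read with it. The repeated-measures ANOVA needs one value per participant and technique, and the ordinary way to obtain it is the mean over that participant's insertions. That agrees with the analysis wording and removes the dependence on count, so the 3.3- to 10-fold figure does not arise.

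The choice between path length and maximum displacement is a fair trade-off. One keeps oscillation and some noise; the other drops oscillation and still grows with time if the tip wanders. No size of bias can be stated from the documents, because they give no sampling rate, jitter or step duration. This conclusion assumes per-insertion averaging. If insertions were summed with counts that differed by technique, the count effect above would be real.

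### The protocol gives two enrolment targets, 50 and 30, and 30 delivers the stated 90% power after dropout only for a one-sided, unadjusted test that is not planned

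*Combined protocol and SAP*

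**What the plan says.** Under Participant Selection Criteria the protocol states "We propose including 50 subjects, 18 years of age and older", and the same paragraph ends "50 subjects are anticipated to be enrolled".

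Under Statistical Methods, Data Analysis, and Interpretation, the sample size is calculated to "detect a mean paired difference of 0.3 (10% of group 1) with an estimated standard deviation of differences of 0.5" between group 1 (one-handed self-advancement) and group 3 (advancement by another person). The conclusion is: "Given a significance level of 0.05 with a power of 90%, and dropout of 10%, we finally targeted the enrollment of 30 participants".

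That section then plans a repeated-measures ANOVA, or a non-parametric equivalent, across the three techniques for the primary outcome. It continues: "And then we will perform the Bonferroni correction for post hoc test". The significance threshold is 0.05. It states neither the sidedness nor the number of corrected comparisons.

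Two other places bear on the reading. Hypothesis 1, in section 4, is directional: "The needle tip will exhibit less movement during catheter advancement when performed by another individual compared to advancement by the inserter". The Analyses paragraph of section 5 mentions "paired t-tests or non-parametric equivalents", again without sidedness.

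**The concern.** There are two linked problems.

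First, 50 and 30 are both enrolment figures. The 30 is said to include dropout already, so it cannot be a completer count set against 50 enrolled. Section 5 says the sample size will come from a power analysis, but the only power analysis given leads to 30.

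Second, the calculation does not say what test it is for. Group 1 versus group 3 is one of three pairs, so under the plan it is tested in the Bonferroni step after a non-directional overall test. If 30 presupposes a one-sided test at an unadjusted 0.05, the calculation describes a different analysis from the one planned.

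At stake are the trial's stated power and the reader's ability to tell when recruitment was meant to end. The protocol allows interim looks and, under Study course item 5, changes to the sample size on interim findings. With two unreconciled targets, nobody can tell afterwards whether stopping at 30 or continuing to 50 was planned or prompted by the data.

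**Working it through.** **Inputs, all from the statistical section:** mean paired difference 0.3 mm; standard deviation of differences 0.5; alpha 0.05; power 90%; dropout 10%. The standardised difference is d = 0.3/0.5 = 0.6.

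**Formulae.** For a paired t-test with n completers, the statistic is noncentral t with n − 1 degrees of freedom and noncentrality 0.6√n. Power is the probability that it exceeds the critical value. Enrolment is n/0.9, rounded up. The normal approximation is n = ((z_alpha + z_power)/d)².

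**Reproducing the plan's 30.** One-sided at 0.05, the smallest n with 90% power is 26 (90.8%), and 26/0.9 = 28.9, so 29 enrolled. This is the only reading tried that lands near 30 once dropout is included. The two-sided normal approximation gives ((1.960 + 1.282)/0.6)² = 29.19, so 30 completers, but 30/0.9 = 33.3, so 34 enrolled. The 30 could therefore be a two-sided figure with the dropout step left out. The documents do not confirm this, and they say dropout was included.

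**Size needed, and power with 30 enrolled.** 30 × 0.9 = 27 completers, noncentrality 0.6√27 = 3.118:

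| Test of group 1 vs group 3 | Completers for 90% | Enrolled for 90% | Power at 27 |
|---|---|---|---|
| One-sided, 0.05 | 26 | 29 | 91.8% |
| Two-sided, 0.05 | 32 | 36 | 85.1% |
| One-sided, 0.05/3 | 35 | 39 | 80.3% |
| Two-sided, 0.05/2 | 38 | 43 | 76.5% |
| Two-sided, 0.05/3 | 41 | 46 | 70.9% |

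The 0.05/3 rows assume that all three pairs are corrected. The 0.05/2 row assumes only the two contrasts against group 3. Even with no dropout, 30 completers give 88.8% two-sided at 0.05 and 76.7% at 0.05/3.

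**Difference detectable with 90% power at 27 completers:** 0.32 mm two-sided at 0.05 and 0.37 mm at 0.05/3, against the planned 0.30 mm.

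**The overall ANOVA.** Assume sphericity and a standard deviation of 0.5 for every pairwise difference, so the error variance is 0.5²/2 = 0.125. The noncentrality is n × (sum of squared deviations of the three means)/0.125, on 2 and 2(n − 1) degrees of freedom. At n = 27:

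- Group 2 midway (0.30, 0.15, 0): 27 × 0.045/0.125 = 9.72, power 77.9%.
- Group 2 equal to group 1 or group 3 (for example 0.30, 0, 0): 27 × 0.060/0.125 = 12.96, power 88.9%.

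A simulation of the full sequence (ANOVA at 0.05, then the pair at 0.05/3, group 2 midway, equal variances and correlations, 40,000 runs) gave 69.6% at 27 completers and 93.0% at 45.

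**If 50 are enrolled.** 50 × 0.9 = 45 completers. Power for group 1 versus group 3 is 97.6% two-sided at 0.05 and 93.3% at 0.05/3.

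**The case against.** The strongest reply is that 30 is not shown to be an arithmetic error. Hypothesis 1 is directional, section 5 mentions paired t-tests, and a one-sided test reproduces about 30. That reading is possible. But no section plans a one-sided test, a directional hypothesis does not by itself specify one, and the section containing the calculation plans non-directional tests with a Bonferroni correction. What stands is that the defect may lie in what the calculation leaves unstated rather than in its arithmetic.

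A second reply is that dividing by three is an assumption and that the ANOVA, not the corrected pair, is the primary test. Both points are fair, and they widen the range. Neither rescues 30: correcting for two contrasts gives 76.5%, and the ANOVA gives 77.9% to 88.9% with group 2 between groups 1 and 3, which is the ordering the plan assumes. At the upper end the ANOVA shortfall is only about one point.

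A third reply is that the theoretical means of 3, 2 and 1 mm imply a 2 mm gap between groups 1 and 3, for which 27 completers are ample. That limits the practical risk. It does not support the stated claim of 90% power at 0.3 mm.

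None of these replies touches the conflict between 50 and 30.

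**Conclusion.** The concern holds on both counts. The 50-versus-30 conflict is plain on the page and needs no calculation. On the plan's own inputs, 30 enrolled with 10% dropout supports 90% power only one-sided and unadjusted. Under the analysis as planned, power for group 1 versus group 3 is 70.9% if the Bonferroni correction covers all three pairs two-sided, and 85.1% on the more lenient two-sided unadjusted reading. These figures rest on the stated difference and standard deviation and on paired t-tests; the ANOVA figures also assume sphericity and equal standard deviations for the pairs.

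If 50 is the true target, power is adequate and the published calculation simply does not describe the trial. If 30 is the target, the power statement must change or a one-sided, unadjusted test must be declared. The correction must be made, because enrolment is a core design quantity and the protocol gives it two values.

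**What to change.** 1. Give one enrolment target in both Participant Selection Criteria and the statistical section.
2. State, for group 1 versus group 3, whether the test is one- or two-sided, the alpha used, and how many comparisons the Bonferroni correction covers.
3. Restate the power to match:
   - **Target 50 (preferred, since it reaches 90% on every reading above):** delete 30 and report, with 45 completers, 97.6% power two-sided at 0.05, or 93.3% at 0.05/3.
   - **Target 30:** delete 50 and report, with 27 completers, 85% two-sided at 0.05, or 71% at 0.05/3. If a one-sided unadjusted test was meant, say so, report 91.8%, and bring the planned analysis into line with it.

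The cost is a wording change in two sections, plus the analysis text if a one-sided test is declared. No participants are needed beyond the 50 already proposed.
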